## Protocol Template

### 1. Study Purpose and Rationale

*Include pertinent background description with references that are related to the need to do this study. If this is a clinical trial, the background should include both preclinical and clinical data. Be brief and to the point.*

The literature regarding analgesic modalities, their combinations and routes of administrations for patients with pain related to renal colic is expanding. Non-steroidal anti-inflammatory drugs (NSAID's) ketorolac and opioids (morphine) constitutes the mainstay of treatment of renal colic either alone or in combinations. Despite their synergism and analgesic superiority when administered together, both classes of these medications possess a set of unfavorable side effects that limit their use. Emerging data of the use of IV lidocaine for patients with renal colic demonstrated good analgesic efficacy and safety profile. However, none of the trials directly compared lidocaine to ketorolac or the combination of both as viable options in patients unable to tolerate or to have serious contraindications to opioids.

### 2. Study Design and Statistical Procedures

*Provide sufficient details so that the adequacy of the statistical procedures can be evaluated including power calculations based on the number of participants to be entered into the study.*

All data will be recorded on data sheets separate from clinical data and entered into Microsoft Excel. The Microsoft Excel spreadsheet will be exported to SPSS 19.0 for statistical analyses. Data will be analyzed by intention to treat and will include frequency distributions, and repeated measures ANOVA to assess a difference in pain scores, and vital signs. The chi-square test will assess the presence or absence of side effects between the three groups. A p-value of < 0.05 will be used to denote statistical significance.

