### 3. Study Procedures

*Describe the procedures in sufficient detail so that a reviewer who is not familiar with them can comprehend what is to be done and can evaluate any risks. Differentiate between procedures that are already being performed for diagnostic or treatment purposes from those that are being done for research, i.e., clearly identify those procedures that would be occurring whether or not the individual was participating in this research.*

We designed a double-blinded, randomized, clinical trial to evaluate analgesic efficacy, safety and feasibility of non-opioid analgesic –IV Lidocaine and IV Ketorolac and combination of both in patients with renal colic. Our hypothesis and proposed study will try to determine if a combination of IV lidocaine and IV ketorolac is superior to either drug alone and if this non-opioid analgesic combination is effective for controlling pain of renal colic origin. The trial will compare pain scores at 15 min and 30 min between and within the three treatment groups of the study: IV ketorolac 30mg push with 10 minute normal saline drip placebo, 1.5mg/kg IV lidocaine drip ( given over 10 minutes) with normal saline push placebo, or IV ketorolac push with IV lidocaine drip.

Once patient is enrolled, the on duty ED pharmacist will prepare any one of the three treatment groups based on a predetermined randomization list generated via SPSS 19.0.17 The study investigators will record pain scores, vital signs, and side effects at baseline, 15, 30 and 60 minutes post-medication administration. If the still patient reports pain of five or greater and requests additional pain relief then morphine at 0.1mg/kg will be given as the rescue analgesic. Blinding of medication from the patient, research team, and staff will be strictly maintained by the pharmacist investigators.

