#### **6. Study Subjects**

*Give detailed inclusion and exclusion criteria and number of participants to be enrolled based on the statistical description and any other considerations. This information should relate to the background information provided above. If this is a clinical trial, this should include a description of the disease and the goals of therapy.*

Patients who will be included in the study are adults aged between 18 and 55 years, clinical diagnosis of acute renal colic, and pain rating of  $\geq 5$  out of 10 on the numerical rating scale. Exclusion criteria includes documented or suspected pregnancy, breastfeeding, contraindication to nonsteroidal anti-inflammatory drugs or lidocaine, known renal dysfunction, received analgesics within 4 hours before presentation, history of bleeding diathesis, history of peptic ulcer disease, current use of warfarin, HR  $< 50$  or  $> 150$ , history of cardiac arrhythmias, peritonitis or presence of any peritoneal sign, altered mental status, weight  $> 100$  kg. We aim to enroll 300 total participants, 100 patients into each study arm.

Nephrolithiasis specifically refers to calculi in the kidneys, but renal calculi and ureteral calculi (ureterolithiasis) are often discussed in conjunction. The majority of renal calculi contain calcium. The pain generated by renal colic is primarily caused by dilation, stretching, and spasm because of the acute ureteral obstruction. The standard of care in the Emergency Department for severe acute renal colic pain control is ketorolac as a single agent or in combination with opioids (morphine). Opioid use is associated with severe nausea and vomiting, sedation and even respiratory depression. Thus, our goal of this project is to evaluate feasibility and analgesic efficacy of medications such as lidocaine. We are evaluating whether the combination of IV lidocaine and IV ketorolac is superior to either drug alone.

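### Pain is to be analysed by repeated measures ANOVA with no stated role for baseline pain as a covariate; adjusting for it costs nothing extra and recovers a modest amount of efficiency

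*Combined protocol and SAP*

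**What the plan says.** Section 2 gives the whole analysis of pain in one clause: "Data will be analyzed by intention to treat and will include frequency distributions, and repeated measures ANOVA to assess a difference in pain scores". It names no model terms, covariates, covariance structure, SPSS procedure or rule for missed scores, and no other section supplies them.

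Section 3 says that the investigators will "record pain scores, vital signs, and side effects at baseline, 15, 30 and 60 minutes post-medication administration". Of these times, two are named for comparison: "The trial will compare pain scores at 15 min and 30 min between and within the three treatment groups of the study". The aim is to "determine if a combination of IV lidocaine and IV ketorolac is superior to either drug alone".

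Section 6 requires entry pain of at least 5 "out of 10 on the numerical rating scale", so every eligible patient should have a baseline score. It sets the size: "We aim to enroll 300 total participants, 100 patients into each study arm". No effect size, SD, correlation, power or missing-data rate is stated.

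**The concern.** The text leaves open how baseline pain enters the arm comparison. Three forms fit it: post-dose scores alone, change from baseline, or an ANOVA in which baseline is one level of the time factor. Which of the first two is more precise depends on the correlation between baseline and follow-up pain, which the sponsor does not give. The third form dilutes the treatment effect if the arm main effect is what is tested, because baseline cannot differ by treatment.

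Using baseline as a covariate removes the need to choose. What is at stake is precision, not bias.

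A secondary and conditional point concerns missed scores. A classical repeated measures ANOVA uses complete rows only. Run that way, it would drop every patient with one missed score in the model, which sits badly with the intention-to-treat analysis promised in the same sentence.

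**Working it through.** **Inputs.** From the documents: 100 per arm (section 6); comparison at 15 and 30 min (section 3); significance at 0.05 (section 2, taken as two-sided). Assumed, because the documents are silent: difference 1.0 point, baseline SD σb = 1.7, follow-up SD σf = 2.8, correlation ρ = 0, 0.3 or 0.5. The plan gives no power figure to reproduce.

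**Variance per patient of each between-arm comparison**
- Post-dose score: σf².
- Change: σb² + σf² − 2ρσbσf.
- Baseline-adjusted: σf²(1 − ρ²).

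Post-dose minus adjusted is ρ²σf². Change minus adjusted is (σb − ρσf)². Neither can be negative, so in large samples adjustment is never worse than either; its cost is one degree of freedom. Change beats post-dose only if ρ exceeds σb/(2σf) = 1.7/5.6 = 0.30.

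**Power for one pair of arms at 30 min.** SE = SD × √(2/100); power = Φ(1.0/SE − 1.960); 95% CI half-width = 1.960 × SE. For example, post-dose: SE = 2.8 × 0.1414 = 0.396, 1.0/0.396 = 2.525, power = Φ(0.565) = 71.4%.

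| | ρ = 0 | ρ = 0.3 | ρ = 0.5 |
|---|---|---|---|
| Post-dose: SD; power; half-width | 2.800; 71.4%; 0.78 | 2.800; 71.4%; 0.78 | 2.800; 71.4%; 0.78 |
| Change: SD; power; half-width | 3.276; 57.9%; 0.91 | 2.806; 71.2%; 0.78 | 2.443; 82.5%; 0.68 |
| Adjusted: SD; power; half-width | 2.800; 71.4%; 0.78 | 2.671; 75.4%; 0.74 | 2.425; 83.0%; 0.67 |
| Gain over the better unadjusted choice (points) | 0 | 4.0 | 0.6 |
| Gain over the worse (points) | 13.5 | 4.2 | 11.6 |

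**Sensitivity to the SDs.** Over baseline SD 1.4, 1.7, 2.0 and follow-up SD 2.4, 2.8, 3.2 (nine combinations), the gain over the better choice stays at 0 to 4 points. Over the worse choice it is 7 to 22 points at ρ = 0, 3 to 10 at 0.3 and 9 to 12 at 0.5.

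**Baseline as a level of time, arm main effect tested.** Take unit SDs, correlation 0.7 between post-dose scores, and an effect of 0.396 SD at all three post-dose times. That effect is (1.960 + 0.842) × √(2/100), the difference that 100 per arm detects with 80% power at one time.
- Averaging four scores shrinks the effect to 0.75 × 0.396 = 0.297, with variance (8.2 + 6ρ)/16 = 0.625 at ρ = 0.3 and 0.70 at ρ = 0.5. Power is 76% and 71%.
- The baseline-adjusted mean of the three post-dose scores has variance 0.8 − ρ² = 0.71 and 0.55. Power is 91% and 97%.
- A simulation of 4,000 trials per setting gave 74% and 71% against 90% and 96%.

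**Missed scores, only if the analysis is listwise.** With each post-dose score missed independently at rate m, the share dropped is 1 − (1 − m)^k for k times in the model. For m = 2% / 5% / 10%:
- k = 2 (15 and 30 min): 4.0 / 9.8 / 19.0%, or 12 / 29 / 57 of 300. Unadjusted 30 min power is 69.7 / 67.0 / 62.3%.
- k = 3 (with 60 min): 5.9 / 14.3 / 27.1%, or 18 / 43 / 81 of 300. Power is 68.8 / 64.7 / 57.8%.
- All available 30 min scores: 70.5 / 69.2 / 66.9%.

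**The case against.** A reader might infer that the planned analysis is invalid or biased. The documents do not support that: arms are randomised, and with complete data the comparison is sound. No power target is stated, so no promised power is lost either.

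Nor do they show that baseline is ignored. Adjustment is unmentioned, not excluded, and the within-group comparison in section 3 more naturally puts baseline into the ANOVA as a level of time. If the arm-by-time test is then used, the comparator is of the change type, and the gain at the central SDs is 13.5 / 4.2 / 0.6 points. This narrows the gain but does not remove it.

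The 22-point figure should not be quoted as likely. It needs baseline SD 2.0, follow-up SD 2.4 and zero correlation. Entry pain is confined to 5 to 10, and a uniform spread over those six scores already has SD √(35/12) = 1.71. The entry cut also lowers the correlation: 0.5 before the cut becomes about 0.40 to 0.47 under assumed baseline distributions.

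It is also fair that these are two-arm figures at one time, not the power of a three-group repeated measures ANOVA. They show the relative precision of the contrasts that answer the stated question.

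Finally, a reader might infer that patients will be dropped. The SPSS procedure is unnamed, the missed-score rate is unknown, and follow-up lasts 60 minutes in one emergency department. With 15 and 30 min in the model, 2% missed costs 70.5 − 69.7 = 0.8 points and 5% costs 69.2 − 67.0 = 2.2. Misses clustered in the same patients would drop fewer. The point stands only as a condition.

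**Conclusion.** The point holds as an improvement in efficiency and specification, not as an error that undermines the trial. Against a sensible unadjusted analysis, baseline adjustment gains 0 to 4 points of pairwise power; against the less suitable one, about 4 to 13.5 points at the central assumptions. The plan does not say which form it will use. That adjustment is no less efficient in large samples does not depend on the assumed values; the size of the gain does, since every SD, correlation, difference and missed-score rate above is assumed. The listwise point is secondary, and the mixed model's answer to it relies on scores being missing at random.

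**What to change.** In section 2, replace repeated measures ANOVA for pain with wording such as:

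> Between-arm differences in pain at 15 and 30 min will be estimated from a linear mixed model with arm, time, arm-by-time, baseline pain and baseline-by-time as fixed effects and an unstructured covariance across times, using all available scores from all randomised patients in the arm assigned. Combination minus ketorolac and combination minus lidocaine will be reported at 15 and 30 min with 95% confidence intervals. Within-group change from baseline will be summarised descriptively for each arm with 95% confidence intervals.

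The last sentence keeps the within-group comparison promised in section 3. The 60 min score is left out of the model because section 3 names only 15 and 30 min for comparison.

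The cost is this wording: same data, no extra measurements, no extra patients. It should be settled before unblinding. It does not decide the primary contrast, multiplicity, or how scores after rescue are counted in the analysis; each needs its own statement.

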#### **13. Potential Benefits**

*This description should also be based on accrued data from related studies that have been completed. There should be a rational description of why such benefits are expected based on current knowledge. If there is unlikely to be direct benefit, describe benefits to society.*

As mentioned above, the goal is relief of acute renal colic pain in the most effective way possible. Our hypothesis that the combination of IV lidocaine and IV ketorolac will result in superior analgesia in comparison to each agent alone and is to be considered as feasible non-opioid analgesics modality for treating patients with renal colic.

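### The claim is that the combination beats each drug alone, but the plan names only a three-group repeated measures ANOVA and does not say which contrasts, at which time, decide it

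*Combined protocol and SAP*

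**What the plan says.** The hypothesis appears three times. Section 3 says the study will try to "determine if a combination of IV lidocaine and IV ketorolac is superior to either drug alone". Section 6 says "We are evaluating whether the combination of IV lidocaine and IV ketorolac is superior to either drug alone". Section 13 expects that "the combination of IV lidocaine and IV ketorolac will result in superior analgesia in comparison to each agent alone".

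The analysis is in section 2. For pain it names "repeated measures ANOVA to assess a difference in pain scores, and vital signs". The chi-square test is reserved for side effects. The threshold is "A p-value of < 0.05 will be used to denote statistical significance".

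On timing, section 3 states: "The trial will compare pain scores at 15 min and 30 min between and within the three treatment groups of the study". It also says the investigators will "record pain scores, vital signs, and side effects at baseline, 15, 30 and 60 minutes post-medication administration".

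The documents do not name a pairwise contrast, a post hoc test, the ANOVA term that decides, a primary time, a way of handling the two times, or a rule that both comparisons must be won.

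**The concern.** Superiority over each component is a statement about two directional differences, and both must favour the combination. A three-group F test asks whether any arms differ, or whether any time courses differ. It can reject because lidocaine alone performs worse, even if adding lidocaine to ketorolac achieves nothing. Section 6 describes ketorolac, alone or with opioids, as standard care, so combination versus ketorolac is the comparison readers most need.

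As the plan stands, two decisions would be made after the data are seen: how to get from a significant F to a superiority conclusion, and whether 15 or 30 minutes carries it.

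**Working it through.** **The plan's own figure.** Section 6 gives 300 patients, and 3 × 100 = 300 agrees. It cannot be checked further, because no power, effect size, SD or dropout is stated.

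**Inputs.** From the documents: three arms of 100, the four recording times, and the 0.05 threshold. Assumed, because the documents give none: follow-up SD 2.8 (range 2 to 3), baseline SD 1.7, correlation 0.7 between follow-up times, correlation 0.3 to 0.5 with baseline, and no missing data.

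**1. How often the F tests reject when the combination equals ketorolac.** Let lidocaine be 1 point worse, so the arm means differ as (0, 1, 0) and the squared deviations sum to 1/9 + 4/9 + 1/9 = 2/3. The group F has 2 and 297 degrees of freedom and noncentrality λ = n Σ(μᵢ − μ̄)² / Var(patient mean).

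- *15 and 30 minutes only.* Var = 2.8² × (1 + 0.7)/2 = 6.664. λ = 100 × (2/3)/6.664 = 10.0. The group F is significant in about 81% of trials. The group-by-time F stays at about 5%, because the deficit is the same at both times.
- *Baseline, 15, 30 and 60 minutes, deficit constant after baseline.* The average deficit is 3/4 = 0.75, so the numerator is 100 × 0.75² × 2/3 = 37.5. Var = [1.7² + 3 × 2.8² + 2(3ρ × 1.7 × 2.8 + 3 × 0.7 × 2.8²)]/16, which is 4.244 at baseline correlation ρ = 0.3 and 4.601 at ρ = 0.5. λ = 8.84 and 8.15, so the group F is significant in about 76% and 72%. By simulation (10,000 trials each, Greenhouse-Geisser correction), the group-by-time F is significant in about 79-90%.

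**2. Two unranked times.** Suppose combination and ketorolac are equal, each time is tested at two-sided 0.05, and either result is accepted. The error is 1 − P(|Z₁| < 1.96 and |Z₂| < 1.96):

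| Correlation, 15 vs 30 min | Two-sided error | In the combination's favour only |
|---|---|---|
| 0.5 | 9.1% | 4.5% |
| 0.7 | 8.3% | 4.2% |
| 0.8 | 7.8% | 3.9% |

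The single-time benchmarks are 5% and 2.5%.

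**3. Requiring both contrasts at one time.** If the combination is no better than ketorolac, the chance of winning both contrasts cannot exceed the chance of winning that one in the favourable direction, which is 0.05/2 = 2.5%. The same holds for lidocaine. No alpha split is therefore needed.

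**4. Power of that rule.** For a true 1-point advantage over both drugs, m = 1/(SD√(2/100)) − 1.96, and joint power is the bivariate normal probability that both contrasts clear the threshold. Their correlation is 0.5, because they share the combination arm. The t column replaces the normal by the t distribution. The last column is a three-group F test at one time, with λ = 100 × (2/3)/SD².

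| SD | m | Joint power, normal | Joint power, t | λ | F-test power |
|---|---|---|---|---|---|
| 2 | 1.576 | 0.900 | 0.898 | 16.67 | 0.962 |
| 2.5 | 0.868 | 0.697 | 0.694 | 10.67 | 0.837 |
| 2.8 | 0.565 | 0.574 | 0.571 | 8.50 | 0.741 |
| 3 | 0.397 | 0.502 | 0.498 | 7.41 | 0.677 |

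**The case against.** The strongest reply is that section 2 should be read with section 3, which commits the trial to group comparisons at 15 and 30 minutes. Pairwise contrasts are a normal output of a three-group repeated measures model. This stands: the chosen method can answer the hypothesis. A reader might infer that the ANOVA is invalid or could never show that the combination beats ketorolac, and the documents do not support that. What remains missing is which comparisons decide, when, and by what rule.

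A second reply is that the F-test percentages are not errors. That also stands. A reader might take 81% as the risk of a false superiority claim. In those scenarios lidocaine really is worse, so a significant F is valid evidence that some arms differ. Harm would arise only if it were reported as superiority over ketorolac, and the documents do not say that it will be.

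Third, the results depend on which times enter the model, which the documents leave open. The group-by-time F is significant in about 5% of trials with 15 and 30 minutes alone, and in 79-90% once baseline and 60 minutes enter. The group F rejects often in both versions, so the qualitative point survives.

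Finally, the trial has other aims. Section 1 notes the lack of a direct lidocaine-ketorolac comparison, and section 3 also asks whether the combination controls pain. A rule for the superiority claim should not demote those aims.

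**Conclusion.** The concern holds as a gap between hypothesis and decision rule. The documents assert superiority over each drug, and the named test, taken at its F statistics, addresses a different hypothesis. The contrasts, the deciding time and the success rule are unstated. This conclusion rests on what the F tests measure and does not depend on the assumed values.

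The sizes do depend on them. With lidocaine 1 point worse, SD 2.8 and the combination adding nothing to ketorolac, the group F is significant in roughly 72-81% of trials, depending on the times included. Leaving both times open raises the two-sided error for combination versus ketorolac from 5% to about 8-9%, at correlations of 0.8 to 0.5. The plan should be amended, but the repeated measures model need not be replaced.

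**What to change.** In section 2, state that:

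- the superiority claim rests on combination versus ketorolac and combination versus lidocaine, estimated from the repeated measures pain model at one prespecified time (15 or 30 minutes, the sponsor's choice);
- the claim is made only if both contrasts reach two-sided p < 0.05 in favour of the combination, with no alpha split;
- baseline pain is, or is not, used in the contrasts;
- for this claim, the F tests and other times are supportive, while ketorolac versus lidocaine and within-group changes are separate aims reported in their own right.

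If both times are to count, require both wins at both times or adjust for the two times. An unadjusted win at either time would bring back the problem.

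The cost is a few sentences, no new data, and some power. For a true 1-point advantage over both drugs, joint power is about 90%, 69%, 57% and 50% at assumed SD 2, 2.5, 2.8 and 3. A one-time three-group F test has 96%, 84%, 74% and 68%, but it answers a different question. Baseline adjustment, which replaces SD by SD√(1 − ρ²), would recover some of this: at SD 2.8, joint power becomes about 62% at ρ = 0.3 and 73% at ρ = 0.5.

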#### **11. Potential Risks**

*Describe risks including data on risks that have been encountered in past studies. That is, if the occurrence of a certain adverse event was 20%, include those data in this description.*

Lidocaine administration is associated with nausea/vomiting, dizziness, periorbital/perioral numbness, tinnitus, slurred speech. These side effects are transient and rapidly reversible. In severe cases, seizures and cardiac arrhythmias might occur; therefore the patient will be placed on the monitor and will be closely and continuously monitored for these side effects. In addition, we will have an antidote ( lipid emulsion) readily available that will be given in case of developing severe side effects.

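### Vital signs are tested only as means and no heart-rate or rhythm event is defined, so a few extreme heart rates on lidocaine could go uncounted

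*Combined protocol and SAP*

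**What the plan says.** Section 2 (Study Design and Statistical Procedures) gives the whole analysis plan. Vital signs share a method with pain: "repeated measures ANOVA to assess a difference in pain scores, and vital signs". Side effects are handled separately, per patient: "The chi-square test will assess the presence or absence of side effects between the three groups". The plan also says "Data will be analyzed by intention to treat and will include frequency distributions", without naming the variables to be tabulated. It does not define or list the side effects, and sets no threshold for any vital sign.

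Section 3 (Study Procedures) makes safety one of the aims. It has vital signs and side effects recorded at baseline and at 15, 30 and 60 minutes, and gives lidocaine over 10 minutes. It lists no separate field for monitor findings.

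Section 11 (Potential Risks) says of lidocaine: "In severe cases, seizures and cardiac arrhythmias might occur; therefore the patient will be placed on the monitor". It then describes continuous monitoring for the side effects it has just listed, so arrhythmia is one of them.

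Section 6 (Study Subjects) excludes patients with "HR $< 50$ or $> 150$ , history of cardiac arrhythmias". These are entry limits. The same section gives the size: "We aim to enroll 300 total participants, 100 patients into each study arm".

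**The concern.** Cardiac toxicity would be expected to show as large changes in a few patients, possibly in both directions: some slow, some fast. An analysis of means spreads a handful of large changes over the whole arm, and opposite changes can cancel. The side-effect comparison would catch those that somebody recognises and records as a side effect. It gives no assurance for a markedly abnormal heart rate without symptoms, or for a rhythm change on the monitor that nobody enters, because the plan does not say whether either counts.

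At stake is the safety conclusion. The report could state that vital signs did not differ between arms while several patients on lidocaine had extreme readings. If a definition is chosen only after the data are seen, the count it yields is open to doubt.

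**Working it through.** The plan gives no figure for cardiac safety, and no power calculation, heart-rate SD or event rate. The only figure to reproduce is the sample size: 3 × 100 = 300, as stated. Two arms contain lidocaine, so 200 patients would receive it.

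**Inputs**
- From the documents: 100 per arm (section 6); significance at 0.05 (section 2), taken here as two-sided.
- Assumed: heart rate is among the vital signs; its SD at one time point is 15 bpm, range 12 to 18; 5 of 100 patients in one lidocaine arm fall by 35 bpm and the rest are unaffected.

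**1. What the mean shows**
- Shift in the arm mean = 0.05 × 35 = 1.75 bpm.
- SE of a difference between two arms = SD × √(2/100). For SD 15 this is 2.12 bpm.
- z = 1.75 / 2.12 = 0.82.
- Power at two-sided 5% ≈ Φ(0.82 − 1.96) = 0.13. For SD 12 it is 0.18; for SD 18 it is 0.11.
- The shift detectable with 80% power at SD 15 is (1.96 + 0.84) × 2.12 = 5.9 bpm, more than three times 1.75.
- Opposite changes: three falls of 35 and two rises of 50 give (−3 × 35 + 2 × 50)/100 = −0.05 bpm, practically nothing.

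This is an unadjusted comparison of two arms at one time. It stands in for one slice of the planned ANOVA and is not the power of that ANOVA.

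**2. A second set of assumptions**

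With 3 of 100 patients changing by 40 bpm, the shift is 3 × 40/100 = 1.2 bpm. Power is 13%, 8% and 6% for SD 10, 15 and 20.

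**3. What counting shows**
- Exact (Clopper-Pearson) two-sided 95% intervals: 5/100 gives 1.6% to 11.3%; 0/100 gives an upper limit of 3.6%; 0/200 gives 1.8%.
- An event with a true rate of 1% appears at least once among 200 lidocaine patients with probability 1 − 0.99^200 = 0.87. At 2% this is 0.98.

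**4. What a test on the counts adds**

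| Ketorolac alone | Lidocaine | Fisher p |
|---|---|---|
| 0/100 | 3/100 | 0.25 |
| 0/100 | 5/100 | 0.059 |
| 0/100 | 10/200 (both arms) | 0.034 |
| 1/100 | 5/100 | 0.21 |
| 1/100 | 10/200 (both arms) | 0.11 |

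| True rates, ketorolac v lidocaine | Fisher power, 100 v 100 | Fisher power, 100 v 200 |
|---|---|---|
| 0% v 3% | 8% | 15% |
| 0% v 5% | 38% | 67% |
| 1% v 5% | 19% | 33% |

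The test is weak for rare events, and one background event on ketorolac moves the pooled p from 0.034 to 0.11. With 0, 5 and 5 events the expected count is 10/3 = 3.3 per arm, which is small for the chi-square approximation, so an exact test is preferable.

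**The case against.** The strongest reply is that cardiac toxicity already has a countable route. Section 11 places arrhythmias among the side effects for which patients are monitored, section 3 records side effects at each time, and section 2 compares them by chi-square. That stands. A reader might infer that the plan judges cardiac safety through the ANOVA of means alone, or that it leaves monitor findings out of the data. The documents support neither. What remains is narrower: the category has no definition, so nothing says whether an abnormal heart rate or an unremarked rhythm change belongs in it. The frequency distributions do not close this gap, since no variables are named.

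A reader might also take 50 and 150 as the protocol's danger limits on treatment. They are entry criteria, and nothing in the documents gives them another role. They are one candidate for an analysis definition, because every eligible patient starts inside them. Someone who starts near 50 could still cross by ordinary variation. Assuming a normal distribution with mean 80 to 85 and SD 15, about 1% to 2.3% of single readings lie below 50.

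The event counts should not be read as the same illustration in another form. A fall of 35 crosses 50 only from a rate below 85. Under the same mean and SD, 37% to 50% of patients start at 85 or above. Zero events on ketorolac is an assumption too. The case for counting is therefore visibility with an honest interval. A non-significant Fisher test could reassure as falsely as the mean does.

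Finally, section 11 names seizures beside arrhythmias and does not call arrhythmia dose-related, so the point should not rest on either idea.

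**Conclusion.** The concern holds in a limited form. Vital signs are analysed only as means, and no heart-rate or rhythm event is pre-specified. Recognised arrhythmias can be counted, but through an undefined category, and an abnormal heart rate outside that category is assured a place only in the mean. Five patients in 100 falling by 35 bpm would be detected at one time point with about 11% to 18% power. That range rests on an assumed SD of 12 to 18 bpm and an assumed pattern of change. The direction does not depend on the exact values: under every set tried for 3 or 5 affected patients, power is well below conventional levels.

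This is worth correcting because safety is a stated aim and the remedy is cheap. It does not show that the trial would miss all cardiac harm, and counting would not turn 100 per arm into a powerful comparison of rare events.

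**What to change.** In section 2, add a per-patient cardiac safety event with two components:
- any post-dose heart rate outside limits that the investigators fix before unblinding (the section 6 entry limits are one candidate);
- any new rhythm disturbance seen on the monitor that section 11 already requires.

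Report the number and percentage of patients with the event in each arm, with exact 95% confidence intervals, as the main output. Add Fisher's exact test of the lidocaine-containing arms against ketorolac alone as supportive. State that its power is low for rare events, so a non-significant result does not show safety. Keep the mean vital-sign analysis as description, and say in the same place how this event relates to the side-effect category.

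The cost is about a sentence of analysis text, one yes/no rhythm field and one more descriptive safety comparison. Vital signs are already collected. One limit remains: heart rates read only at 15, 30 and 60 minutes may miss brief changes during the 10-minute infusion. The rhythm field covers these only in part. This is an analysis definition and changes no treatment rule.
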